## 6.7.3 Food and Fluid intake

Subjects will be provided food and non-alcoholic beverages by the CTU during the dosing period of the trial. Subjects will fast at least 6 hours prior to blood draw on days of clinical laboratory testing (screening, Day -2, Day 1 [pre-dose], Day 2, Day 3 and Day 14 [ $\pm$  3 days]). Subjects will fast for at least 6 h before dosing on Day 1 and 2 h after dosing. In addition, subjects will fast from 4 hours before to at least 2 hours after bronchoscopy. A light nutritional broth or beverage may be served if bronchoscopy is scheduled 4 h to 8 h after dosing on Day 1. Water can be taken *ad lib* during those periods of fasting. Water consumption will be at least 2 L daily from the time of dosing to 48 h (Day 2) after dosing, and the time and amount consumed will be recorded.

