## 7.4 Baseline (Day -1)

Admitted subjects will have the following assessments:

- Review inclusion/exclusion criteria, before 12-lead ECGs, to confirm the subject remains eligible for enrollment.
- Update MH.
- Update Prior Medications.
- Obtain VS.
- Perform abbreviated PE.
- Assign subject to Lung PK timepoint cohorts (T1-T4) and enroll in Advantage eClinical®.
- Obtain baseline 12-lead standard ECG with 10-sec rhythm strip in triplicate at the same timepoints as the projected timepoints for ECGs to be recorded before and after dosing on Day 1 (within 30 min before and 1 h [± 5 min], 4 h [± 10 min], and 16 h [± 15 min] after start of dosing).
- Counsel to avoid rigorous physical activity, encourage good hydration, avoid caffeinated beverages.

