#### Dosing:

- Administer a single 30 mg/kg body weight dose of apramycin as a single IV infusion with a syringe or infusion pump over 30 (± 5) minutes in a forearm vein, as described in Section 6.2.
- Initiate TEAE assessments (excluding laboratory events) and SAE assessments.
- Perform focused PE (for TEAE assessments).

- Initiate recording of ConMeds.
- Withhold food until 2 h after end of dosing or 2 h after end of scheduled bronchoscopy according to subject assignment into one of the Lung PK cohorts (T1-T5).
- Allow access to water.

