- 10. The CKD-EPI equation, expressed as a single equation, is  $GFR = 141 \times min(Scr/\kappa, 1)\alpha \times max(Scr/\kappa, 1)-1.209 \times 0.993 Age \times 1.018$  [if female] \_ 1.159 [if black], where Scr is serum creatinine,  $\kappa$  is 0.7 for females and 0.9 for males,  $\alpha$  is -0.329 for females and -0.411 for males, min indicates the minimum of Scr/ $\kappa$  or 1, and max indicates the maximum of Scr/ $\kappa$  or 1 [Levey 2009].(Formula will be used and result will be included in the lab report)
- 11. Urinalysis (UA) by dipstick. If abnormal for blood, protein and glucose, perform microscopic UA. The results of microscopic UA supersede those of UA by dipstick. UA may be postponed in a menstruating female. Abnormal UA in a menstruating female is not graded as a TEAE; the UA should be completed after the end of menstruation.
- 12. Cystatin C in serum.
- 13. Kidney-injury molecule 1 (KIM-1) in urine.
- 14. Ear otoscopy, Valsalva test, tympanometry, stapedial reflexes, and pure-tone audiometry with standard frequencies and distortion product otoacoustic emissions (DPOAEs) at screening. Ear otoscopy, and pure-tone audiometry including high frequencies and DPOAEs at check-in (Day -2 [or Day -4 or Day -3 if needed]) and at Days 3 (+2 days), 14 (± 3 days), and 30 (± 4 days), or ET.
- 15. Subjects will be admitted to the ward on Day -2 after confirmation of eligibility.
- 16. Assignment to Lung PK timepoint cohorts (T1 T5) and Enrollment to be performed before 12-lead ECG on Day -1. Subjects with ECGs on Day-1 and pre-dose on Day 1 with clinically significant abnormalities according to the PI should not be eligible for receiving study drug and should be withdrawn and replaced.
- 17. Subjects may be discharged from the CTU after Day 3 collection of the 60-h plasma PK sample.
- 18. Duration of a ramycin infusion is  $30 \pm 5$  min.
- 19. Adverse events from the start of dosing to the end of the trial are considered treatment-emergent adverse events (TEAE) or serious AEs (SAE).

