#### **3.3.3.** Baseline

Baseline for clinical laboratory, VS, and audiology results will be defined as the last value recorded before administration of study drug.

For ECG measurements, pre-dose baseline is defined as the last value recorded before administration of study drug, and time-matched baseline is defined as the value recorded at the same timepoint on the day before administration of study drug (Day -1) as on Day 1. If triplicate ECG measurements were performed, the mean value of the ECG measurements will be used as the pre-dose and time-matched baseline values.

Baseline height, weight, and body mass index (BMI) will be the measurements obtained at Screening. Age will be based on age at the time of enrollment.

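### The time-matched ECG contrast does not match meal state: at 1 h all 20 subjects are fasting by rule on Day 1, but Day -1 has no meal condition

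*Protocol*

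**What the plan says.** **Day 1.** Protocol 6.7.3 states: "Subjects will fast for at least 6 h before dosing on Day 1 and 2 h after dosing". It then adds a second window: "In addition, subjects will fast from 4 hours before to at least 2 hours after bronchoscopy". One exception is given: "A light nutritional broth or beverage may be served if bronchoscopy is scheduled 4 h to 8 h after dosing on Day 1". The Day 1 dosing procedures in 7.5.1 put the end of the fast differently: "Withhold food until 2 h after end of dosing or 2 h after end of scheduled bronchoscopy", depending on cohort.

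**Day -1.** Protocol 7.4 schedules triplicate ECGs "at the same timepoints as the projected timepoints for ECGs to be recorded before and after dosing on Day 1", that is, at the clock times of pre-dose, 1 h, 4 h and 16 h. The only instructions to subjects there concern activity, hydration and caffeine. Section 6.7.3 also states: "Subjects will fast at least 6 hours prior to blood draw on days of clinical laboratory testing". It lists those days as screening, Day -2, Day 1, Day 2, Day 3 and Day 14, so Day -1 is not covered. Section 8.1.7 requires at least 5 min of supine rest before an ECG and says nothing about food. Neither schedule of events adds a Day -1 meal condition.

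**Analysis.** In SAP 3.3.3, "time-matched baseline is defined as the value recorded at the same timepoint on the day before administration of study drug". Protocol 11.4.6.1 uses delta-delta QTcF to measure QTcF prolongation. SAP 9.8 reports the time-matched change for each ECG parameter with a 90% CI (Tables 63/64). It also reports the change from the Day 1 pre-dose value (Tables 61/62).

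**The concern.** SAP 4.2 confirms that there is no control group, so the Day -1 recordings are the only means of removing within-day variation from the Day 1 ECGs. That works only if the two days differ in drug and in little else. Caffeine, vigorous activity and supine rest are controlled on both days. Food is controlled on one.

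The 1 h recording matters most. It falls about 30 min after the end of a 30-min infusion and is the scheduled ECG closest to peak plasma exposure. If subjects ate before the matching Day -1 recording, any effect of that meal on heart rate, PR or QTcF would appear in Tables 63/64 as a post-dose change, and the plan has no way of separating the two. These intervals are secondary outcomes (Protocol 3.2.2). The gap cannot be closed after the data are collected unless meal times were recorded.

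**Working it through.** The plan gives no ECG sample-size figure to reproduce. Twenty subjects were chosen on clinical judgment, and no SD or effect size is stated. The check therefore sets the fasting windows against the ECG times and then looks at precision.

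**1. Meal state by rule on Day 1.** Times are hours from the start of infusion.
- Dosing fast: from -6 to 2 h (Protocol 6.7.3), or to 0.5 + 2 = 2.5 h if counted from the end of a 30-min infusion (7.5.1).
- Bronchoscopy fast: from (BAL time - 4) to at least (BAL time + 2).

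| Cohort (4 each) | BAL | Bronchoscopy fast | ECG at 1 h | ECG at 4 h |
|---|---|---|---|---|
| T1 | 0.5 | -3.5 to at least 2.5 | fasting | may have eaten from about 2.5 h |
| T2 | 2 | -2 to at least 4 | fasting | fasting, at the end of the window |
| T3 | 4 | 0 to at least 6 | fasting | fasting, broth allowed |
| T4 | 8 | 4 to at least 10 | fasting | boundary: food possible from about 2 to 2.5 h, fast starts at 4 h |
| T5 | 24 (nominal) | 20 to at least 26 | fasting | may have eaten from about 2 to 2.5 h |

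Counts under a required fast:
- Pre-dose and 1 h: 5 x 4 = 20 of 20.
- 4 h: 2 x 4 = 8 of 20 (T2, T3), or 12 of 20 if T4 is counted.
- 16 h: 0 of 20.
- Day -1, at any of the four matched times: 0 of 20 by rule.

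**2. Which analyses are exposed.**
- Time-matched (Tables 63/64): the Day 1 value minus the Day -1 value at the same timepoint. At 1 h this is a required fast minus an unspecified state.
- Pre-dose baseline (Tables 61/62, with the interpretation and categorical tables 55-58 and 65-68): at 1 h this is fasted minus fasted. At 4 h it can carry a meal difference in cohorts that have eaten by then.

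**3. Precision of the mean change.** SAP 9.8 gives the 90% CI half-width as t(n-1, 0.95) x SD / sqrt(n). The SD is an assumption here.
- n = 20, SD 8 ms: 1.729 x 8 / 4.472 = 3.1 ms.
- n = 20, SD 12 ms: 1.729 x 12 / 4.472 = 4.6 ms.
- n = 16 (T5 not enrolled), SD 8 and 12 ms: 1.753 x 8 / 4 = 3.5 ms and 1.753 x 12 / 4 = 5.3 ms.

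**4. Sensitivity only.** Suppose a fixed fed/fasted shift applied to all 20 subjects at 1 h, with an assumed SD of 10 ms (standard error 10 / 4.472 = 2.24 ms). By the noncentral t distribution with 19 df, the nominal 90% CI would contain the true drug effect in 77.7%, 30.5% or 3.6% of trials for an assumed shift of 2, 5 or 8 ms. The documents support none of these shifts. The figures show only how the interval behaves if such a shift exists.

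**The case against.** The strongest reply is that the plan already has a meal-consistent analysis at 1 h. The change from Day 1 pre-dose is reported with its own 90% CI, and the categorical QTcF, PR, QRS and HR tables use that baseline. This stands. A reader might infer that all ECG changes at 1 h and 4 h mix a meal effect with the drug effect, but the documents do not support that: the exposure at 1 h is confined to the time-matched contrast. The pre-dose analysis is still not a full substitute, because it leaves within-day variation in place, which is what the Day -1 recordings were added to remove.

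A second reply is that nothing shows that subjects ate before the Day -1 ECGs. The manual of procedures, which is not among the documents, may set meals. This also stands. Being an inpatient with no stated fast does not establish a fed state.

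A third is that no meal effect is given, so any bias in milliseconds is assumed. At 2 ms it would be smaller than either half-width for n = 20. A reader might conclude that the bias equals or exceeds the stated uncertainty, but that follows only from the shift one chooses to assume.

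A fourth is that meal matching would not isolate a drug effect. T1 has bronchoscopy under sedation or light anesthesia before its 1 h ECG, and T2 before its 4 h ECG; Day -1 has neither. This is correct and belongs in the report. It limits what the fix achieves but does not make the meal mismatch harmless in the other cohorts at 1 h.

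Finally, the ECG outcomes are descriptive and secondary, and no halting rule refers to the time-matched contrast. That limits the consequence.

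**Conclusion.** The gap is real and limited. At 1 h, the time-matched ECG contrast compares a required fast in 20 of 20 subjects with an unspecified meal state. At 4 h the mismatch depends on cohort, so it should not be read as fasted versus fed throughout. By 16 h no Day 1 fast applies. Because the Day 1 state changes over the day, no single constant correction to the time-matched results would remove a meal difference.

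Whether a meal effect is present, in which direction and how large, cannot be determined from the documents. The half-widths of 3.1 to 4.6 ms rest on an assumed SD of 8 to 12 ms and only give the scale against which a shift would matter. The conclusion also assumes that no document outside the protocol and SAP already fixes Day -1 meals. It is worth acting on because the remedy is cheap and the data cannot be repaired afterwards.

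**What to change.** In Protocol 6.7.3 and 7.4, have subjects follow on Day -1 the same fasting period and meal clock times as planned for Day 1: the dosing-fast window for all cohorts, then the meal times of the planned cohort. This is workable because subjects are inpatients from Day -2 and cohort assignment comes first ("Enrollment to be performed before 12-lead ECG on Day -1", Appendix A, Table 1, footnote 16).

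Record actual meal times on both days. Protocol 5.3.1 allows reassignment to another cohort on the day of bronchoscopy, and the record would show whose 4 h meal state no longer matches. The 1 h match survives reassignment, because the dosing fast is common to all cohorts.

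Sections 6.7.3 and 7.5.1 must be reconciled on when the dosing fast ends, so that Day -1 can mirror one rule.

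When Tables 63/64 are reported, state that T1 at 1 h and T2 at 4 h also differ from Day -1 by sedation and bronchoscopy, which meal matching does not remove. If Day -1 meals cannot be aligned, report these tables with the meal-state limitation.

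The cost is a few sentences in the protocol, a unit meal schedule and a meal-time entry. No procedure or sample is added. The downside is one more fasted morning per subject.

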## 6.7.4 Alcohol, Marijuana and Illicit Drugs

Subjects will have to agree to consume not more than 24 g (men)/ 12 g (women) pure alcohol per day from Screening to enrollment (Day -2) and from the day of discharge from the CTU on Day 3 to Day  $30 \pm 4$  days (final visit). Alcohol will not be served during the in-patient period

from Day -2 check-in to Day 3. Marijuana and illicit drugs are prohibited during the course of the trial.

#### 6.7.5 Caffeinated beverages

Caffeinated beverages or foods containing caffeine are prohibited within 48 hours before dosing to Day 3 of the trial. On other days, consumption is restricted to not more than 3 cups or equivalent per day.

#### 6.7.6 Exposure to loud noise

Subjects have to avoid exposure to loud noise (e.g., construction sites, visiting concerts or dance events, fireworks, listening to music or playing videogames with headphones) from screening until Day  $30 \pm 4$  days (final visit).

## 7 STUDY SCHEDULE

The Schedule of Study Procedures and Evaluations is included as Appendix A.

## 7.1 Recruitment

The subject population will be recruited from the local population surrounding the CTU, utilizing the CTU subject database and IRB-approved advertisements and social media. IRB-approved, prescreening questionnaires will be used to determine if subjects meet study requirements before scheduling screening visits.

#### 7.2 Screening Visit (Day -28 to Day -3)

This will be an out-patient visit to complete the following within 28 days before study drug dosing:

**Note:** A second screening visit may be scheduled to complete Otoacoustic screening tests to accommodate subjects' personal schedule.

- Obtain informed consent.
- Assign a study ID number to subjects who consent to participate.
- Record demographics including age, gender, race, and ethnicity.
- Obtain contact information.
- Obtain height and body weight, and calculate Body Mass Index (BMI; wt [kg] / ht [m^2])
- Take VS (supine and resting for at least 5 min systolic and diastolic BP [SBP and DBP], heart rate [HR], respiratory rate [RR], and oral temperature [T]).
- Obtain Medical History (MH).
- Review history of Prior Medications.
- Perform complete Physical Examination (PE).
- Obtain blood and urine samples for screening clinical laboratory tests that include a calculation of Glomerular Filtration Rate (GFR) by the CKD-EPI equation.
- Obtain blood samples for viral serology (HIV antibody, HBsAg, HCV antibody).
- Obtain serum for β-HCG pregnancy test from all women.
- Obtain serum for FSH level from only post-menopausal women.
- Obtain urine sample for illicit drugs and drugs of abuse (urine drug screen), and cotinine.
- Perform alcohol breathalyzer test.
- Obtain a single 12-lead ECG with 10-sec rhythm strip.
- Perform spirometry.
- ENT Examination that includes:
  - Ear Otoscopy.
  - Valsalva test.

- Tympanometry.
- Stapedial Reflexes.
- Cochlear (Hearing) Examination that includes:
  - Ear Audiometry (pure tone audiometry).
  - o Distortion Product Otoacoustic Emissions (DPOAEs).
- Counsel on use of contraception (males and females), avoidance of pregnancy (women of childbearing potential), avoidance of prohibited medication, illicit drugs, alcohol, nicotine products, vigorous exercise, and exposure to loud noises).
- Confirm eligibility.

Subjects who meet the eligibility criteria of the otoacoustic assessments will be contacted by CTU personnel and asked to return on Day -2 to complete check-in assessments and be admitted to the CTU if they continue to meet eligibility criteria.

Subjects who fail screening due to a medical condition or abnormal laboratory tests including pregnancy test and positive tests for HIV, HBV, and HCV will be informed of the findings and counseled to seek medical care for further evaluation and treatment. If subjects test positive for HIV antibody, HBsAg, and/or HCV antibody, they will be informed that test results may be reported to the local health authorities according to state or local law.

Subjects who fail the otoacoustic screening will be informed of the findings and counseled to seek medical care by an otolaryngologist or audiologist for further evaluation and treatment.

Subjects who fail screening assessments on either one of these visits will not be rescreened unless they had an inter-current, short-term medical illness. Subjects who meet eligibility criteria but could not be enrolled within permissible window may be rescreened.

## 7.3 Check-in (Day -2)

Subjects meeting all inclusion and no exclusion criteria at Screening Visit will check into the CTU on Day -2 and the following procedures will be performed:

- Review inclusion/exclusion criteria to confirm the subject remains eligible for admission.
- Update MH.
- Update Prior Medications.
- Obtain VS.
- Obtain body weight.
- Perform complete PE.
- Obtain blood and urine samples for clinical laboratory tests that include a calculation of GFR by the CKD-EPI equation (for determining eligibility).

- For all women, a urine β-HCG pregnancy test will be done, and negative results confirmed before dosing.
- Obtain urine sample for illicit drugs and drugs of abuse (urine drug screen) and cotinine.
- Perform alcohol breathalyzer test.
- Obtain sample for serum Cystatin-C.
- Obtain sample for urinary KIM-1.
- Obtain a single 12-lead ECG with 10-sec rhythm strip.
- Perform otoacoustic assessments.
  - Ear otoscopy.
  - Audiometry (pure tone audiometry including high frequencies).
  - DPOAEs.

Note: Day -2 otoacoustic assessments may be completed on Day -4 or Day-3 as if needed.

- Admit eligible subjects in the CTU.
- Counsel to avoid rigorous physical activity, encourage good hydration, avoid caffeinated beverages and exposure to loud noises.

## 7.4 Baseline (Day -1)

Admitted subjects will have the following assessments:

- Review inclusion/exclusion criteria, before 12-lead ECGs, to confirm the subject remains eligible for enrollment.
- Update MH.
- Update Prior Medications.
- Obtain VS.
- Perform abbreviated PE.
- Assign subject to Lung PK timepoint cohorts (T1-T4) and enroll in Advantage eClinical®.
- Obtain baseline 12-lead standard ECG with 10-sec rhythm strip in triplicate at the same timepoints as the projected timepoints for ECGs to be recorded before and after dosing on Day 1 (within 30 min before and 1 h [± 5 min], 4 h [± 10 min], and 16 h [± 15 min] after start of dosing).
- Counsel to avoid rigorous physical activity, encourage good hydration, avoid caffeinated beverages.

## 7.5 Inpatient Treatment Period (Days 1 to 3)

#### 7.5.1 DAY 1: Administration of Study Drug – Bronchoscopy (Cohorts T1 – T4)

Before Dosing:

- Withhold breakfast or food at least 4 hours before scheduled post-dose bronchoscopy, according to subject assignment into one the Lung PK cohorts (T1-T5).
- Allow access to water.
- Review inclusion/exclusion criteria to confirm the subject remains eligible for dosing.
- Update MH.
- Update Prior Medications and review any new medication.
- Obtain VS within 30 min before dosing (baseline).
- Perform symptom-directed PE.
- Obtain 12-lead standard ECG with 10-sec rhythm strip in triplicate within 30 min before dosing.
- Insert IV catheter for blood collection into a hand or forearm vein.
- Insert IV line for study drug infusion into a vein in the other forearm.
- Obtain blood and urine samples for clinical laboratory tests that include a calculation of GFR by the CKD-EPI equation (for baseline).
- Obtain sample for serum Cystatin-C (for baseline).
- Obtain sample for urinary KIM-1 (for baseline).
- Obtain pre-dose blood (plasma) PK sample for total apramycin within 30 min before starting administration of study drug.
  - Measure pre-dose urea concentration in an aliquot of the blood 9plasma) PK sample collected within 30 min before starting administration of study drug.
- Note 1: *If 12-lead standard ECGs, VS assessments, and PK blood draws to be done at the same timepoint before or after dosing, these procedures will be performed in this order: 12-lead standard ECG, VS, and PK blood draw.*
- Note 2: In cohort T3, obtain ECG, VS and PK draws at the 4 h timepoint before administration of sedation or anesthetic for BAL.
- Note 3: CTU staff may complete pre-dosing procedures in the bronchoscopy ward instead of the CTU to enable timely initiation of bronchoscopy at 0.5 h ( $\pm$  5 min) after initiation of the dosing in subjects assigned to cohort T1.

#### Dosing:

- Administer a single 30 mg/kg body weight dose of apramycin as a single IV infusion with a syringe or infusion pump over 30 (± 5) minutes in a forearm vein, as described in Section 6.2.
- Initiate TEAE assessments (excluding laboratory events) and SAE assessments.
- Perform focused PE (for TEAE assessments).

- Initiate recording of ConMeds.
- Withhold food until 2 h after end of dosing or 2 h after end of scheduled bronchoscopy according to subject assignment into one of the Lung PK cohorts (T1-T5).
- Allow access to water.

#### After Dosing:

- Bronchoscopy with BAL once per subject at the following nominal timepoints after starting IMP infusion according to the assigned cohort: 0.5 h (± 5 min) (T1),
   2 h (± 5 min) (T2). 4 h (± 10 min) (T2) and 8 h (T4) (± 15 min)
  - 2 h (± 5 min) (T2), 4 h (± 10 min) (T3) and 8 h (T4) (± 15 min).
  - Transfer subject to the UTMC bronchoscopy suite accompanied by CTU staff.
    Note: Subjects in T1 may start receiving study drug in the bronchoscopy suite.
  - Collect scheduled safety information before and after the procedure in the bronchoscopy suite and during the recovery period.
  - Monitor subject before and after the procedure per orders by the bronchoscopy and anesthesia services.
  - Transfer subject to the CTU from the UTMC bronchoscopy suite accompanied by CTU staff.
  - Collect BAL samples for the measurement of total apramycin concentration and estimate of PK parameters once per subject at the assigned timepoint above, as described in Section 8.5, corresponding to the assigned cohort: 0.5 h (± 5 min) (T1), 2 h (± 5 min) (T2), 4 h (± 10 min) (T3) and 8 h (T4) (± 15 min) after initiation of dosing. Details on processing the BAL samples and preparation of ELF and AM samples for apramycin concentration measurements and PK analysis will be provided in the MOP.

Note 1: Collect plasma samples for total apramycin concentration within 5 min of the corresponding BAL procedure at 0.5 h ( $\pm$  5 min),

2 h ( $\pm$  5 min), 4 h ( $\pm$  10 min), or 8 h ( $\pm$  15 min) after initiation of the infusion. If collection of BAL samples is delayed, plasma samples will be collected at the indicated nominal timepoint (and allowable windows), as described above, and an additional plasma PK will be collected within 5 min after the last BAL sample. Note 2: Measure urea concentration at the same timepoint as the nominal timepoint of plasma PK or in the plasma sample that is collected within 5 min after the last BAL sample if BAL is delayed.

- Obtain the bronchoscopy Procedure Record. Data to be transcribed from procedure record onto study CRF will be described in the MOP.
- Check infusion site (during and end-of-infusion, and 1 h ( $\pm 5$  min) and 16 h ( $\pm 15$  min) after the infusion for infusion site reactions. Details will be provided in the MOP.
- Obtain 12-lead standard ECG with 10-sec rhythm strip in triplicate at 1 h (±5 min), 4 h (±10 min) and 16 h (±15 min) after dosing. Record ECG before VS and PK draws and, at 4 h, before administration of sedation or anesthetic for BAL in cohort T3.

- Obtain VS at 1 h ( $\pm 5$  min), 4 h ( $\pm 10$  min) and 16 h ( $\pm 15$  min) after dosing:
  - Note: More frequent monitoring will be at the PI's discretion based on subject's clinical status after bronchoscopy.
- Obtain blood (plasma) PK samples for total apramycin at 0.5 h (±5 min, immediately at the end of infusion), 1 h (±5 min), 2 h (±5 min), 4 h (±10 min), 8 h (±15 min), and 16 h (±15 min) after initiating the IMP infusion.
  - Note 1: An aliquot of plasma PK collected at 0.5 h (±5 min; immediately after the end of infusion) after starting the IMP infusion will be used for the protein binding test (for measurement of free apramycin).
  - Note 2: An aliquot of plasma PK collected at 0.5 h ( $\pm 5 \text{ min}$ ) after starting the IMP infusion will be used for the measurement of urea.
- Monitor subject closely until fully recovered per bronchoscopy instructions.
  - Provide oxygenation as needed.
- Perform TEAE assessments (excluding laboratory events) and SAE assessments.
- Document ConMeds.
- Do not provide solid food until at least 2 h after bronchoscopy and the subject is able to swallow.
- Encourage water intake at least 2 L daily Document time and volume consumed.
- Counsel to avoid rigorous physical activity and avoid caffeinated beverages.

